9.3. Protocol deviations and violations

Protocol deviations from monitoring reports and other relevant sources will be tabulated by

type of protocol deviation (whether the deviation is major or minor) using the ITT population

by study part and treatment group. Listings will present all protocol deviations and violations

by study part, treatment group and subject. Any violation of the inclusion/exclusion criteria

will be reported in accordance with the policy and procedures of the IEC/IRBs at participating

study sites.

9.4.Demographics and baseline characteristics

Subject demographics and baseline characteristics will be summarized by study part and treatment group using the ITT and mITT populations, if there is a difference between the populations. Information to be summarized includes age in years, gender, race, ethnicity, weight, miglustat status (Yes/No), NPC-SS Score category (10-19, 20+), duration of neurological symptoms at baseline (years), duration of neurological symptoms at baseline (<4 years, 4-8 years, >8 years), seizures (Yes/No), and baseline NPC-SS total score, NPC-SS total score minus hearing components and NPC-SS composite endpoint score.

9.5.Medical history

Relevant medical history, including history of current disease, pertinent respiratory history, and information regarding underlying diseases will be coded using Medical Dictionary for Regulatory Activities (MedDRA, version 18.0). Medical history will be summarized by system organ class (SOC) and preferred term (PT) by study part and treatment group using the mITT population. All medical history data will also be listed.

9.6.NPC disease history

NPC disease history, including occurrence of NPC related medical conditions or procedures (yes or no), medication used to treat NPC or symptoms associated with NPC (yes or no), and family history of NPC (yes or no) will be summarized by study part and treatment group using the mITT population.

10. Study drug and other medications

10.1.Prior and concomitant medications

All concomitant medications collected from screening through the end of the study will be classified by drug class and PT according to the World Health Organization (WHO) Drug Dictionary. Prior medications are any medications taken prior to the first dose of study medication (i.e., start date and end date occurs before the first study medication dose date). If the medication start date is completely missing, then the medication will be considered as

August 27, 2018

Page 30

concomitant unless it can be determined that the medication end date occurred prior to the first dose of study medication. If the medication start date is partially missing and the partial date is not sufficient to determine if the medication was taken after the first dose of study medication, then the medication will be considered concomitant for the study unless it can be ruled out by the partial date and/or medication end date.

The number and percent of safety subjects using concomitant medications will be tabulated by drug class, study part and treatment group. All prior and concomitant medications will be listed.

10.2.Duration of treatment and exposure to study drug

Duration of treatment will be defined as the length of time from first dose of study administration to date of discontinuation from the study treatment within each study part (Part A/B combined and Part C). That is, (Date of last dose during study part treatment period – Date of first dose of study drug during study part + 1 day). Exposure to VTS-270 will be calculated as the total dose (mg) received during the study part (Part A/B combined or Part C). Standard descriptive statistics will be used to summarize duration and exposure by study part and treatment group using the safety analysis set.

Compliance to study medication will be calculated as 100 × (number of times a subject received study medication)/(Expected number of times a subject was to receive study medication per the protocol schedule while participating in the trial). Compliance will be calculated separately for each study part (A/B combined and C). All dosing information will be listed by study part, treatment group and subject ID. Study drug administration over time will be summarized in a listing showing VTS-270 dose at each scheduled clinic visit and/or IT administration.

11. Efficacy analyses

The statistical methods described below apply to the analyses performed for Part B. All Part C data will only be listed and summarized.

VTS301: STATISTICAL ANALYSIS PLAN August 27, 2018 Page 31

11.1.Co-primary efficacy analyses

The co-primary efficacy endpoints are as follows:

- Change from baseline in NPC-SS composite score at Week 52 in the group treated with VTS-270 vs. the sham control group
- The Blinded Clinician CGIC at Week 52 in the group treated with VTS-270 vs. the sham control group

The NPC-SS composite score is the sum of the ambulation, cognition, fine motor, and swallowing domains of the NPC-SS. This outcome ranges in value from 0 to 20 points at each assessment. Measurements at baseline, each post-baseline measurement through Week 52, and change from baseline for each measurement through Week 52 will be summarized descriptively. For the co-primary efficacy analysis, any missing Week 52 assessments will be imputed. Subjects who take the rescue option will be considered dropouts and will need to have their missing Week 52 assessment imputed. To protect against the potential bias that may occur if outcomes for the completers are different from those for the non-completers (i.e., missing not at random; MNAR), the approach taken will be to impute all missing observations from either treatment arm as if they came from the sham group. That is, the average change from baseline for the sham group will be added to the baseline observation of each subject with a missing assessment at Week 52. The missing value imputation will occur at the individual domain level. An ANCOVA, with treatment group, study part, and baseline NPC-SS composite score included in the model, will be performed to test for differences in the change from baseline to Week 52 between VTS-270 and sham groups in the co-primary efficacy outcome measure. Considering the small sample size, this ANCOVA will be performed using a nonparametric approach such that the outcome data will be ranked. Average ranks will be assigned in case of ties. The null hypothesis will be $H_0: \Delta_d - \Delta_s = 0$, and the alternative hypothesis will be H₁: Δ_d - $\Delta_s \neq 0$, where Δ_d is the mean rank of the change from baseline for the drug VTS-270 group and Δ_s is the mean rank of the change from baseline for the sham group. The null hypothesis will be tested with both means adjusted for study part in which the subject was randomized to (A or B) and baseline NPC-SS composite score. This test will be performed at α =0.05 level (two-sided) of significance.

August 27, 2018

Page 32

The analysis of the blinded Clinician CGIC at Week 52 will be conducted using the nonparametric Van Elteren method to test for the treatment effect using study part as a blocking variable. Average ranks will be assigned when there are ties within a block. Missing Week 52 assessments will be imputed. To protect against the potential bias that may occur if outcomes for the completers are different from those for the non-completers (i.e., MNAR), the approach taken will be to impute all missing observations from either treatment arm as if they came from the sham group. That is, the average blinded Clinician-CGIC at Week 52 for the sham group will be imputed for each subject with a missing assessment at Week 52. Because the average value of the sham group used for imputation may not be an integer, but needs to be in order to fit the ordinal categories of the blinded Clinician-CGIC, the ceiling (worst case) will be applied to the average value before imputation.

11.2. Sensitivity analyses for the co-primary endpoints

In order to determine if the conclusions from the co-primary efficacy analyses are robust, several sensitivity analyses will be conducted.

First, the ANCOVA of the NPC-SS composite score co-primary endpoint will be repeated using the raw, unranked change from baseline to Week 52 data. Missing data will be imputed as described above. The Shapiro-Wilk test for normality will be performed to test the normality assumption.

Second, the co-primary efficacy analyses will be repeated using the PP population, assuming there are differences between the mITT and PP populations. Missing values in the PP population will be imputed in the same way as described above for the co-primary efficacy analyses.

Third, the co-primary efficacy analyses will be repeated excluding the 6 subjects randomized to the 1200 mg and 1800 mg dose levels in Part A.

Fourth, the co-primary efficacy analyses will be repeated excluding the 3 subjects from site because subjects from this site had extremely poor adherence to the protocol.

Fifth, the proportion of Clinician CGIC responders (defined as a score of no change, minimally improved, moderately improved, or markedly improved) at Week 52 will be analyzed using the Cochran-Mantel-Haenszel (CMH) test, stratified by the following stratification groups:

- Subjects randomized in Part A
- Subjects randomized in Part B, miglustat use +, NPC-SS total score ≥ 20
- Subjects randomized in Part B, miglustat use -, NPC-SS total score ≥ 20
- Subjects randomized in Part B, miglustat use +, NPC-SS total score < 20
- Subjects randomized in Part B, miglustat use -, NPC-SS total score < 20

11.3.Key secondary endpoints and analyses

[figure not shown]
The following key secondary endpoints comparing VTS-270 treated subjects with the sham controls will be analyzed using a hierarchical testing, serial gatekeeping strategy based on the mITT population.

- Proportion of Clinician CGIC responders (defined as a score of no change, minimally improved, moderately improved or markedly improved) at Week 52
- Change from baseline to Week 52 in the NPC-SS total score with the hearing domain and ABR modifiers removed
- Proportion of responders (defined as no change or improvement) on NPC-SS total score with the hearing domain and ABR modifiers removed, at Week 52

A serial gatekeeper testing strategy will be used to protect the overall type I error rate of 0.05 (two-sided). These key secondary efficacy endpoints will be tested only if both co-primary efficacy null hypotheses described in Section 11.1 have been rejected, thus maintaining the overall significance level at 5% (two-sided). Each family will be tested at α =0.05 level (two-sided) provided all analyses in the preceding families were significant (Figure 1).

August 27, 2018 Page 34

Figure 1. Serial Gatekeeper Strategy

The analysis of the proportion of Clinician CGIC responders (defined as a score of no change, minimally improved, moderately improved, or markedly improved) at Week 52 will be conducted using the CMH test, stratified by study part. Missing Week 52 assessments will be imputed using similar methods to the co-primary efficacy analysis methods prior to determining responder status. The analysis and resulting p-value will be considered exploratory if either of the co-primary efficacy endpoints is not statistically significant at α =0.05 level (two-sided).

The NPC-SS total score, excluding the hearing domain and ABR modifier results, will be analyzed in the same way as the co-primary efficacy endpoint using ranked data. Missing data at Week 52 and dropouts will be handled using the same methods as for the co-primary efficacy endpoint. The analysis and resulting p-value will be considered exploratory if the

key secondary efficacy endpoint analysis of proportion of Clinician CGIC responders is not statistically significant at α =0.05 level (two-sided).

The NPC-SS total score, excluding the hearing domain and ABR modifier results, will be evaluated by a responder analysis to assess whether the VTS-270 group had a greater average response compared to the sham group. Missing Week 52 values will be imputed in the same way as described above prior to determining responder status. The responder analysis will consist of a tabulation of the number and percent of subjects falling into the predefined categories, and a CMH test, stratified by study part, will be performed to examine any difference between the treatment groups. The analysis and resulting p-value will be considered exploratory if the secondary efficacy endpoint analysis of change from baseline to Week 52 in total NPC-SS, excluding the hearing domain and ABR modifier, is not statistically significant at α =0.05 level (two-sided).

For sensitivity analyses, the above key secondary endpoint analyses will be repeated using the PP population, assuming there are differences between the mITT and PP populations.

Missing values in the PP population will be imputed in the same way as described above for the key secondary efficacy endpoint analyses.

11.4.Other secondary endpoints and analyses

The following other (non-key) secondary endpoints will be performed to assess the treatment effect using the mITT population. The tests will be non-hierarchical and type I error will not be adjusted for multiple testing.

- Proportion of Caregiver CGIC responders (defined as a score of no change, minimally improved, moderately improved or markedly improved) at Week 52 will be analyzed using a CMH test, stratified by study part, to assess for any differences in the group treated with VTS-270 vs. the sham control group.
- Responses to the EQ-5D-3L proxy questionnaire following 52 weeks of treatment for VTS-270 treated subjects compared to sham controls will also be summarized by study part and treatment group using appropriate descriptive statistics.

August 27, 2018

Page 36

 Percentage of subjects who qualified for the rescue option in the VTS-270 group compared to sham-treated subjects, following a minimum of 26 weeks of treatment, will be analyzed using the CMH test, stratified by study part.

- Change from baseline to Week 52 in each of the 9 clinical domains of the NPC-SS in the group treated with VTS-270 vs. the sham control group will be analyzed using nonparametric methods similar to the co-primary endpoint analysis.
- Change from baseline to Week 52 in the total NPC-SS, with hearing domain and ABR
 modifier included, in the group treated with VTS-270 vs. the sham control group will be
 analyzed using nonparametric methods similar to the co-primary endpoint analysis.
- Time to event analyses time to increase in NPC-SS composite of 1 or more (worsening).
 The product-limit survival analysis method will be used to estimate the time to event of interest and Cox's proportional hazards model will be used to assess the treatment effect on hazard ratios (HRs) adjusted for study part.
- The composite NPC-SS mean annualized rate of change (slope) from baseline to Week 52 will be analyzed using nonparametric methods similar to the co-primary efficacy endpoint analysis. In this case, the rank of the slope [365.25 * ((measurement at post-baseline visit measurement at baseline)/(date of post-baseline visit date of baseline visit + 1))], rather than the change from baseline at Week 52 in the composite NPC-SS score, will be the dependent variable in the model.
- TUG test results following 52 weeks of treatment compared to baseline for VTS-270
 treated subjects compared to sham controls will be analyzed using methods similar to the
 co-primary endpoint analysis. Where several assessments are made at the same visit, the
 average of the test results will be used for analysis.
- 9-hole peg test results following 52 weeks of treatment compared to baseline for VTS-270 treated subjects compared to sham controls will be analyzed using methods similar to the co-primary endpoint analysis. Where several assessments are made at the same visit, the average of the test results will be used for analysis.

VTS301: STATISTICAL ANALYSIS PLAN August 27, 2018 Page 37

11.5.Multiplicity

A hierarchical, serial gatekeeper testing strategy will be used to protect the overall type I error rate of α =0.05 (two-sided) when testing the co-primary endpoints together with the key secondary endpoints (as described in section 11.3). No adjustment for multiplicity will be performed for testing the other (non-key) secondary endpoints.

11.6.Exploratory endpoints and analyses

The following analyses will be performed for exploratory purposes:

- The co-primary efficacy NPC-SS composite analysis will be repeated based on a completers analysis where subjects missing week 52 assessments will remain missing.
- The co-primary efficacy NPC-SS composite endpoint analysis will be performed
 assuming data missing at random (MAR). A standard multiple imputation will be
 implemented using separate imputation models for the VTS-270 and sham groups.
 Only the baseline and week 52 assessments will be included in the analysis.
- The co-primary efficacy NPC-SS composite endpoint analysis will be performed using a
 pattern mixture model. Only the baseline and week 52 assessments will be included in
 the analysis.
- Individual level outcomes applied to each of the NPC-SS composite domains following 52 weeks of treatment for VTS-270 treated subjects compared to sham controls. Each individual level outcome will be assigned the value of +1 if the change from baseline is negative (i.e., the subject improves over time), 0 if the change from baseline is 0, and -1 if the change from baseline is positive (i.e., the subject declines over time). The analysis of the individual-level outcome will be based on the exact likelihood ratio test to test the null hypothesis that the values are the same across the two groups. The analysis will be applied to each of four composite domains of the NPC-SS scores separately.
- The proportion of subjects that are responders (defined as a score of 0 or +1) on each
 domain (ambulation, cognition, fine motor, swallowing) of the NPC-SS composite will
 be analyzed using the CMH test, stratified by study part.

 Cross-tabulation analysis of Clinician CGIC responders (defined as a score of no change, minimally improved, moderately improved, or markedly improved) and individual NPC-SS composite domain responders (defined as no change or improvement) at Week 52.

11.7.Subgroup analyses

Subgroup analyses will be performed on the following efficacy endpoints:

- Change from baseline in NPC-SS composite score at Week 52
- Blinded Clinician CGIC at Week 52
- Change from baseline in NPC-SS total score at Week 52
- Change from baseline in NPC-SS total score minus hearing and ABR at Week 52
- Change from baseline in individual scores for the 9 domains of the NPC-SS score at Week 52
- Composite NPC-SS mean annualized rate of change (slope) from baseline at Week 52

The endpoints above will be summarized by treatment group for the subgroups defined on the basis of the categorized variables listed below:

Grouping variable	Subgroups
Baseline Miglustat use	Yes,
	No
Baseline NPC severity	<20,
	≥20
Duration of neurological	<4,
symptoms at baseline (years)	4-8,
	>8
Post-baseline Miglustat use	Yes,
	No
Clinician-CGIC severity	Minimally worse,
	Moderately worse,

	Markedly worse

12. Safety summaries

All of the assessments in the sections below will be performed both for Part B using the Safety population and Part C using the Part C Open-Label population.

12.1.Adverse events

Adverse events will be coded using the most current version of MedDRA and summarized by SOC, PT, and worst National Cancer Institute Common Terminology Criteria for Adverse Events (NCI CTCAE version 4.03) grade per subject.

Investigators will assess the relationship of each adverse event to study drug. The relationship of each adverse event to study drug will be categorized as not related, unlikely related, possibly related, probably related, and definitely related.

12.1.1. Hearing AEs of special interest

There are two types of possible hearing impairment AEs – subjective and objective AEs. **Subjective events** will be reported to the AE assessor during their interaction with the subject/family (i.e. hearing impairment associated with spoken language, tinnitus, turning up the TV, functional concerns, etc.). **Objective events** will be identified by the Audiologist during the audiologic evaluation. Objective hearing impairment AEs are identified by assigning a CTCAE or ABR Adverse Event grade at every Audiologic evaluation after screening/baseline. A modified CTCAE scale is used to grade audiologic evaluations obtained through behavioral audiometry. An ABR Adverse Event Scale is used when behavioral audiometry is not obtainable, and an Auditory Brainstem Response test is used to determine hearing thresholds.

August 27, 2018

Page 40

The following is a modified grading system, derived from the CTCAE (v4.03) scale that will be

used to determine the AE grade for hearing impairment when hearing thresholds are obtained

via pure tone audiometry:

Grade 1: (on a 1, 2, 3, 4, 6 and 8 kHz audiogram): Threshold shift >20 dB at 8 kHz in at

least one ear.

Grade 2: (on a 1, 2, 3, 4, 6 and 8 kHz audiogram): Threshold shift >20 dB at 4 kHz and

above in at least one ear.

• Grade 3: (on a 1, 2, 3, 4, 6 and 8 kHz audiogram): hearing impairment sufficient to

indicate therapeutic intervention, including hearing aids; threshold shift >20 dB at 3 kHz

and above in at least one ear; additional speech-language related services indicated.

Grade 4: Decrease in hearing to profound bilateral impairment (absolute threshold >80

dBHL at 2 kHz and above); non-serviceable hearing

The following is the "ABR Adverse Event Scale" (developed specifically for use in VTS301)

that will be used to determine the AE grade for hearing impairment when hearing thresholds

are obtained via diagnostic ABR not using pure tone thresholds:

Grade 1: Threshold shift >10 < 20 dB at 4 kHz in at least one ear

Grade 2: Threshold shift >20 dB at 4 kHz in at least one ear

• Grade 3: Threshold shift >20 dB at 2 kHz in at least one ear

• Grade 4: Absolute thresholds >80 dBeHL from 1-4 kHz (not previously present at

baseline) bilaterally

12.1.2.AE summaries

All AE presentations will summarize treatment emergent adverse events (TEAEs) defined as

adverse events with onset on or after randomization or onset prior to randomization but with

worsened severity post-randomization. In case of partially missing AE start and stop dates,

the dates will be imputed by comparing to first dose date of study medication so that the

corresponding AEs will be made treatment-emergent whenever possible, unless the available

partial date information clearly indicates that the event happened outside of the treatment

CONFIDENTIAL

period. In general, a conservative strategy will be followed with respect to the assignment of AEs with partial start dates.

Presentations for Part A/B will include all adverse events with an onset date through the first Part C dose date - 1. Presentations for Part C will include all adverse events with an onset date on or after the first VTS-270 dose date. The incidence of TEAEs will be shown in terms of the total number of subjects and not in terms of the total number of events.

The following presentations of treatment-emergent adverse events will be summarized by study part and treatment group:

- Serious adverse events
- All adverse events
- Adverse events by greatest toxicity grade (greatest severity will be used where toxicity grade is missing)
- Adverse events ≥ Grade 3 toxicity (severity will be used where toxicity grade is missing)
- Adverse events related to study drug (i.e., AEs classified as possibly, probably, and definitely related)
- Adverse events related to LP procedure (Adverse events were categorized as 'related to LP procedure' if the event was marked as related to intrathecal procedure or other protocol required procedures.)
- Adverse events of special interest: Related to or resulting in hearing impairment, and seizures, other agitation, aphasia, dystonia and other neurologic AE's.
- Adverse events leading to study discontinuation.

All of the above summaries, other than the AEs related to study drug summary, will be repeated based on related AEs. All AEs will be listed with MedDRA coding, onset and resolution dates, seriousness, severity, relationship, actions, and outcome.

In addition, the adverse events for subjects who took study medication from batch will be summarized to evaluate any impact of the decrease in pH over time.

August 27, 2018

Page 42

The following subgroup analyses will also be performed.

• Treatment emergent adverse events by SOC, PT, and post-baseline Miglustat use (yes,

no)

Treatment related treatment emergent adverse events by SOC, PT, and post-baseline

Miglustat use (yes, no)

Treatment emergent serious adverse events by SOC, PT, and post-baseline Miglustat

use (yes, no)

12.2.Deaths

The number of subjects who died will be summarized by treatment regimen. A by-subject

listing of deaths will include death date, cause of death, and relationship to study treatment.

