12.5. Laboratory data

Exhibit 2 – Exhibit 7 displays the timing of laboratory tests. Clinical laboratory values and

changes from baseline will be summarized by study part, treatment group and time point.

Laboratory data will be summarized by presenting shift tables from baseline to each post-

baseline time point. Figures may be used if appropriate.

12.6.Audiologic evaluation

Audiologic evaluations were used as exploratory clinical endpoints as well as additional safety

measurements assessing ototoxicity. The audiologic evaluations performed over the course of

the study included: behavioral assessment of pure tones and speech measures (threshold and

word discrimination), tympanometry, otoacoustic emissions, and ABR. Pure tone assessment

(Air Conduction and Bone Conduction) will be summarized as it best captures possible

ototoxicity.

Air conduction (AC) was tested at the following frequencies: 250 Hz, 500 Hz, 1000 Hz,

2000 Hz, 3000 Hz, 4000 Hz, 6000 Hz, and 8000 Hz. Bone conduction (BC) was tested at the

following frequencies: 250 Hz, 500 Hz, 1000 Hz, 2000 Hz, and 4000 Hz. Descriptive statistics

of hearing thresholds in decibels will be presented by study part, treatment group, conduction

type, visit, frequency and ear.

Pure tone averaging was done for both AC and BC across low frequencies of 500 Hz, 1000 Hz,

and 2000 Hz. Pure tone averaging will also be done for AC at high frequencies of 4000 Hz,

6000 Hz, and 8000 Hz. If at least two non-missing thresholds are obtained per conduction type

and ear, the pure tone average (PTA) for AC and the bone conduction average (BCA) for BC

will be calculated by adding up the threshold levels in decibels (dB), and then dividing the

sum by the number of thresholds obtained. PTA and BCA will be summarized by study part,

treatment group, visit and ear.

CONFIDENTIAL

August 27, 2018

Page 44

A diagnostic ABR was tested at the following frequencies: 500 Hz, 1000 Hz, 2000 Hz, and 4000 Hz. Descriptive statistics of hearing thresholds in decibels will be presented by study part, treatment group, visit, frequency and ear.

When conducting the PTA and ABR, the sites recorded the type of hearing impairment and hearing impairment severity. Hearing impairment severity was categorized as follows (more than one could apply to a subject at each assessment).

- Normal hearing (-10 to 15 dB)
- Slight hearing impairment (16 to 25 dB)
- Mild hearing impairment (26 to 40 dB)

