Severe dysmetria/dystonia (gross motor limitation, requires assistance for self-care activities)	5	Minimal cognitive function	5

August 27, 2018 Page 48

Table A1. NPC Clinical Severity Scale, co	ntinued		
Hearing (sensorineural)	Score	Memory	Score
Normal hearing (all tones ≤ 15 dB HL)	0	Normal	0
High frequency hearing loss (PTA** \leq 15 dB HL, >15 dB HL in high frequencies)	1	Mild short-term or long-term memory loss	1
Slight-mild hearing loss (PTA 16-44 dB HL)	2	Moderate short-term or long-term memory loss (gets lost)	2
Moderate hearing loss (PTA 45-70 dB HL)	3	Difficulty following commands	3
Severe hearing loss (PTA 71-90 dB HL)	4	Unable to follow commands or short- and long-term memory loss	4
Profound hearing loss (PTA > 90 dB HL)	5	Minimal memory	5
Seizures	Score		
No history of seizures	0		
Hx of single seizure	1		
Rare seizures	2		
Seizures, well controlled with meds	3		
Seizures, difficult to control with meds	5		
Modifiers			
Gelastic Cataplexy	Score	Hyperreflexia	Score
No history	0	None	0
Definitive history	+1	Mild (3+)	+1
Frequent (every month)	+2	Severe (+ clonus)	+2
Narcolepsy	Score	Incontinence	Score
No history	0	No problems	0
Definitive history	+1	Occasional	+1
Frequent (every month)	+2	Frequent	+2
Behavior	Score	ABR	Score
No problems	0	Normal	0
Hx of ADHD, aggressive	+1	Abnormal	+1
Harmful to self/others	+2	Absent	+2
Psychiatric	Score	Respiratory	Score
No problems	0	No problems	0
Hx of mild depression	+1	Hx pneumonia	+1
Hx of major depression, hallucinations, or psychotic episodes	+2	Pneumonia ≥ 2x/year or active therapeutic intervention	+2

^{*}Score is additive within these two subsections

^{**}Pure tone average reported on the audiogram

August 27, 2018 Page 49

13.2.Schedule of Assessments

Exhibit 2. Study Parts A and B schedule of assessments (Screening through Week 26)

Visit Number		1	2	3	4	5	6	7	8	9	10	11	12	13	14
Study Day	Day -45 to Day -1	0	14	28	42	56	70	84	98	112	126	140	154	168	182
Window (days)			(±3)	(±3)	(±3)	(±3)	(±3)	(±7)	(±7)	(±7)	(±7)	(±7)	(±7)	(±7)	(±7)
Time Point (Week)	Screening	1 st Study Dose	2	4	6	8	10	12	14	16	18	20	22	24	26
Study Procedure															
Informed consent	X														
Demographics, medical hx ^a	X														
Medication history	X														
Collect urine ^b	X					X#		X						X	
Pregnancy test	X														
Physical exam ^c	X													X	
Vital signs	X ^d	X ^{d,e}	X ^{d,e}	X ^{d,e}	X ^{d,e}	X ^{d,e}	X ^{d,e}	$X^{d,e}$	X ^{d,e}						
Weight	X														

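### As printed, the SAP's ABR hearing scale gives no grade to a 4 kHz threshold shift of exactly 20 dB, although it grades 15 dB

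*SAP*

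**What the plan says.** SAP 12.1.1 separates subjective hearing events, which are reported to the AE assessor, from objective ones found by the audiologist. For the objective ones, "Objective hearing impairment AEs are identified by assigning a CTCAE or ABR Adverse Event grade at every Audiologic evaluation after screening/baseline". Two scales are given. A modified CTCAE scale serves pure tone audiometry; "An ABR Adverse Event Scale is used when behavioral audiometry is not obtainable".

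The ABR scale has these limits:

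- The lowest grade is printed with two strict limits: "Grade 1: Threshold shift >10 < 20 dB at 4 kHz in at least one ear".
- The second grade keeps the same frequency and has one strict lower limit, printed as follows: "Grade 2: Threshold shift >20 dB at 4 kHz in at least one ear".
- The third grade looks at 2 kHz instead and also requires more than 20 dB.
- Grade 4 is set by absolute thresholds above 80 dBeHL in both ears and is not a shift criterion.

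SAP 12.6 confirms that 4 kHz is measured: "A diagnostic ABR was tested at the following frequencies: 500 Hz, 1000 Hz, 2000 Hz, and 4000 Hz". SAP 12.1.2 tabulates AEs by greatest toxicity grade and lists hearing impairment among the AEs of special interest. Neither document gives a rule for a shift of exactly 20 dB.

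**The concern.** Grades 1 and 2 of the ABR scale use the same frequency and differ only in the size of the shift, so their limits should meet. As printed, both exclude 20 dB. The scale therefore does not rise steadily: a smaller shift counts as an objective adverse event and a larger one does not.

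This matters because SAP 12.6 treats ototoxicity as a known risk of the study drug. The ABR scale is the objective grading route for subjects who cannot complete behavioral audiometry. The SAP says the scale was developed for this trial, so it points to no parent instrument that would settle the boundary.

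**Working it through.** The documents give no figure to reproduce here. The check is to apply the printed limits to possible shifts.

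**Inputs (SAP 12.1.1, signs taken as printed).** Let s4 and s2 be the shifts in dB at 4 kHz and 2 kHz.

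- Grade 1: 10 < s4 < 20
- Grade 2: s4 > 20
- Grade 3: s2 > 20
- Grade 4: absolute bilateral thresholds above 80 dBeHL

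**Step 1. One ear, s2 not above 20, Grade 4 not met.**

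| s4 (dB) | As printed | If Grade 1 read ≤20 | If Grade 2 read ≥20 |
|---|---|---|---|
| 10 | none | none | none |
| 11, 15, 19 | 1 | 1 | 1 |
| 20 | **none** | 1 | 2 |
| 21, 25, 30 | 2 | 2 | 2 |

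Among whole-dB shifts from 11 to 60, 20 is the only ungraded value. The missing grade at 10 dB is the lower limit of the scale, not a gap between grades.

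**Step 2. Other routes to a grade for a subject with 20 dB at 4 kHz in one ear.**

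- Other ear shifted by 0 or by 20 dB: no grade.
- Other ear shifted by more than 10 and less than 20 dB: Grade 1.
- Other ear shifted by more than 20 dB: Grade 2.
- 2 kHz shift above 20 dB: Grade 3.
- Absolute thresholds qualify: Grade 4.

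**Step 3. How attainable is 20 dB?** The step size is not in the documents, so it is an assumption. Count the attainable shifts above 10 and up to 20 dB:

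- 1 dB steps: 11 to 20, which is 10 values, of which 1 is ungraded.
- 5 dB steps: 15 and 20, which is 2 values, of which 1 is ungraded. The sequence 15, 20, 25 gives Grade 1, none, Grade 2.
- 10 dB steps: 20 only, and it is ungraded. Grade 1 could never occur.

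These are counts of possible values, not of subjects.

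**Step 4. The pure tone scale.** Its shift-based grades (1 to 3) all use a shift above 20 dB and differ by frequency, so it has no matching gap between grades.

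**The case against.** **The gap may not be in the source.** An underlined less-than sign can lose its line when a PDF is converted to text. Inclusive signs survive elsewhere, for example "Normal hearing (all tones ≤ 15 dB HL" in Appendix 13.1, but that shows only that true ≤ characters survive. The Grade 1 line is also oddly spaced: there is a space before its 20, and none in the >20 limits nearby. This objection stands until the page is checked.

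**An ungraded shift is not a lost hearing event.** A reader might infer that such a subject has no hearing AE at all. The documents do not support that. The routes in Step 2 remain open, and subjective events need no ABR grade. SAP 12.6 also plans ABR threshold summaries by treatment group, visit, frequency and ear, impairment-severity summaries, and listings of all audiometry. What can be lost is an event in the AE count, not the measurement.

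**Efficacy is untouched.** The unblinding sensitivity analysis in SAP 12.6 uses clinically manifest hearing AEs from the blinded AE rater and hearing-aid recommendations, not the ABR grade. This is correct.

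**Re-derived grades are not ordinary AEs.** The audiologist identifies objective events, and investigators assess relationship (SAP 12.1). A grade computed later would lack that assessment. This stands and shapes the fix.

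**Conclusion.** The point holds as a boundary error in the printed scale. On the 4 kHz criterion alone, a 20 dB shift is not identified as an objective hearing AE, while a 15 dB shift is. This is a wrong result from the stated rule, not just missing detail.

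Its practical size cannot be stated. The step size, the number of subjects graded by ABR and the number of 20 dB shifts are all absent from the documents, and the count could be zero. The conclusion assumes that the signs are as printed.

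A reader might infer that the gap hides events mainly on VTS-270. That would be plausible given the known ototoxicity and the larger planned active arm (35 against 16, SAP 8.5), but no count in the documents shows it. Co-primary analyses, alpha and power are unaffected.

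**What to change.** 1. Check the Grade 1 symbol on the source page of SAP 12.1.1. If it reads ≤20, the point closes.
2. If it does not, the sponsor should make the two grades contiguous by stating which one includes 20 dB. Writing ≤20 in Grade 1 leaves every other >20 dB limit in that section unchanged; writing ≥20 in Grade 2 also closes the gap. The documents do not settle the choice.
3. Apply the corrected scale to the recorded ABR thresholds at all post-baseline evaluations. Report any newly graded shifts in a flagged supplementary hearing-AE table by treatment group, separate from the investigator-reported AEs.

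The cost is a one-symbol correction and a small tabulation from data already held. In Parts A and B the schedule has ABR only at screening, Week 8 (Part A subjects), Week 52 and early termination; in Part C it is roughly yearly. The drawback is that the re-derived events carry no investigator-assessed relationship, which the table should state.
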